15.2 Individually randomized trials in Phase A

For all studies, the community-level inclusion/exclusion criteria, individual-level inclusion/exclusion criteria, recruitment process, study interventions, and study procedures have previously been described. Briefly in each trial, consenting participants will be randomized in a 1:1 ratio to the intervention or standard-of-care. Blocked randomization will be stratified on site and further stratified by sex for certain trials enrolling both sexes. All analyses of Dynamic Prevention in Phase A will restrict to participants enrolled before September 1, 2021.

The primary outcome for the individual-level prevention trials will be biomedical covered time defined as the proportion of follow-up time that the participant is protected from HIV infection with either PrEP or PEP. Follow-up time for the primary outcome will be over 48 weeks; follow-up time will be censored at HIV seroconversion, death, or withdrawal. Secondary and sensitivity analyses will examine alternative definitions of covered time, including restricting follow-up to periods of self-reported HIV risk.

The primary outcome for the individual-level treatment trials is an indicator of viral suppression (HIV RNA<400 cps/mL). The primary outcome is viral suppression at 48 weeks for the mobility intervention trial and 24 weeks for the alcohol intervention trial. In both trials, the primary analysis will exclude individuals who die or withdraw during follow-up; the alcohol intervention study will additionally exclude participants who move out of the study region. In the primary analysis, participants who do not have a viral load measurement within the ascertainment window will be assumed to be un suppressed; secondary analyses will adjust for incomplete ascertainment of viral loads. Additional sensitivity analyses will assess the robustness of these analytic choices.

The primary outcome for the hypertension linkage trial is an indicator of linkage to hypertension care by 30 days. The primary definition will rely on clinical records; individuals without records will be assumed to never have linked. To assess the impact of the voucher, we will

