15.3 Cluster randomized trials for Phase A

For the VHT cluster randomized trial (CRT), the community-level inclusion/exclusion criteria, individual-level inclusion/exclusion criteria, recruitment process, study interventions, and study procedures have previously been described. Briefly, N=16 villages (served by VHTs) will be randomized in a 1:1 ratio to the intervention or standard-of-care, after matching on country. Within each cluster, participants will be consented and enrolled in the measurement cohort if HIV-uninfected and at risk of HIV acquisition. Analyses of the VHT trial will restrict to participants enrolled before September 1, 2021.

The primary outcome for the cluster-level prevention trial will be biomedical covered time, defined as in the individually randomized prevention trials. As before, follow-up time for the primary outcome will be over 48 weeks; follow-up time will be censored at HIV seroconversion, death, or withdrawal. Secondary and sensitivity analyses will examine alternative definitions of covered time, including restricting follow-up to periods of self-reported HIV risk.

Prevention coverage will be compared between arms using a TMLE, adapted to appropriately account for the dependence of outcomes within clusters.^{5, 106 107} Given the limited number of clusters, we will use Adaptive Pre-specification to optimally adjust for covariate imbalance between randomized arms, while preserving Type-I error control.¹⁰⁸ In secondary analyses, we will implement the unadjusted estimator as the contrast of the average arm-specific outcomes. We will

test the **null hypothesis** that the Dynamic Prevention did not improve prevention coverage, as compared to standard-of-care, with a two-sided test at the 5% significance level.

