This Appendix describes the continuation of the 3 Dynamic Prevention Randomized studies (refer to section 9.2.1 of protocol) for a 48 week follow up period following re-consent for this CAB-LA extension. Persons who are already enrolled in the trials and were randomized to the intervention arm will be eligible to receive CAB-LA as one of the options in the “Dynamic prevention” model. Persons in the control arms will be eligible to receive CAB-LA if and when it is rolled out through in country programs. If CAB-LA is not available in country at the 48-week endpoint, all participants in the intervention arm will have the opportunity to continue in the study until Week 96, and participants who are currently on CAB-LA may continue through the extension. The study will end at Week 96, and by that time participants will be transitioned to in country prevention care. At 96 weeks, persons on CAB-LA will be transitioned to in country CAB-LA or to other prevention options if CAB-LA is not available. Prior to this transition, available in country options will be assessed by the study team. HIV prevention options will be discussed with each study participant by their Week 88 visit, with a plan established for the transition to the participant’s preferred prevention method in coordination with local health facilities to avoid interruption after their 96 weeks of study participation is completed.

The overall purpose of this extension is to 1) Determine if adding the option of CAB-LA as a prevention choice using a patient-centered HIV prevention delivery model increases prevention coverage (i.e. proportion of time that is covered by a biomedical prevention option, such as PrEP or PEP) compared to the standard-of-care in 3 ongoing randomized trials of Dynamic Choice Prevention in rural Uganda and Kenya; and, 2) Conduct a hybrid implementation study (Primary Objective Clinical and Secondary Objective Implementation) focusing on initial implementation of a patient-centered model for CAB-LA using the RE-AIM evaluation framework among persons randomized to the intervention arms.

A. Background and Rationale

Background: SEARCH Sapphire is an ongoing, NIH-funded study that is testing multi-disease and multi-sector interventions aimed at reducing HIV burden and improving health in rural Uganda and Kenya. Phase A is a portfolio of randomized prevention and treatment implementation studies that will inform a population-level study in Phase B (refer to section 3.0 of protocol).

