This appendix describes a 48-week extension of 3 ongoing randomized trials in Phase A studying a patient-centered “Dynamic Choice Prevention” (DCP) implementation strategy for delivering existing evidence-based biomedical prevention interventions vs. standard of care (SOC). The Dynamic prevention model offers participants choices on prevention modality on an ongoing basis: oral PrEP, or oral PEP, and the option to switch between products. The trials are being conducted in 3 settings: antenatal (ANC) clinics, the outpatient department (primary care clinics), and in rural community settings in Western Kenya and Uganda (refer to section 9.2.1 of protocol). All clinic and village health team staff (i.e., Clinical Officers, nurses, coordinators, health workers) are trained and equipped for HIV prevention care in the clinical setting, appropriate to their role (refer to section 9.2.1.1 of the protocol).

In the CAB-LA extension, participants in the intervention and control arms are reconsented and remain in their initial randomized arm. Persons in the intervention arms who remain HIV

negative will be offered CAB-LA as an additional biomedical prevention option, if eligible. CAB-LA will be delivered at health clinics. The primary 48-week endpoint for this extension is proportion of time covered by a biomedical prevention product. As of May 9, 2022, a total of 1213 HIV-negative persons aged 15 years and older and at risk for HIV acquisition were enrolled in the studies. (Table 1). New participants are being enrolled at the present to time to replace those participants who have moved and have been unable to continue in the CAB-LA study. The total number of participants in the study eligible for CAB-LA will not exceed the 593 listed in Table 1.

Table 1. Enrollment in 3 SEARCH Sapphire Dynamic Prevention Trials as of May 9, 2022

Dynamic Prevention Study	Intervention and Control, (N) Uganda	Intervention (N) Uganda	Intervention and Control, (N) Kenya	Intervention (N) Kenya	Total Enrolled (N), Intervention and Control	Total Enrolled Intervention (N)
Antenatal/SRH Clinic	200	100	201	103	401	203
Outpatient Department Clinics	201	100	201	97	402	197
Household Study Community Village Health Team (VHT)	200	83	210	110	410	193
All Trials Together	601	283	612	310	1213	593

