Population: The persons eligible for participation in the extension are those who were enrolled in the 3 ongoing trials. Persons for the ANC study are recruited and enrolled through offering study participation at ANC clinics at government sponsored health facilities. Persons for the Outpatient department are recruited and enrolled through offering study participation at Outpatient department clinics at government sponsored health facilities. Persons for the community study are recruited via home visits by village health teams/community health workers (refer to section 7.5.1 of protocol).

Inclusion criteria for the Extension include:

- 1) Enrollment in a SEARCH Sapphire Dynamic prevention study
- 2) HIV negative at start of extension
- 3) Residing in study region

Additional inclusion criteria to access CAB-LA as a prevention option

- 1) Not pregnant at time of initial CAB-LA injection
- 2) Participant weighs at least 35kg

Additional Exclusion Criteria to access CAB-LA as a prevention option

- 1) Participant has Hepatitis B or chronic Hepatitis C Diagnosis
- 2) Participant has ALT ≥ 5 ULN
- 3) Participant has clinical history of liver cirrhosis or current clinical evidence of cirrhosis or severe liver disease
- 4) Previous hypersensitivity reaction to cabotegravir

- 5) Receiving the following co-administered drugs for which significant decreases in cabotegravir plasma concentrations may occur due to uridine diphosphate glucuronosyltransferase:
 - i. Anticonvulsants: Carbamazepine, oxcarbazepine, phenobarbital, phenytoin
 - ii. Antimycobacterials: Rifampin, rifapentine
- 6) Participants with a current or anticipated need for chronic systemic anticoagulation or a history of known or suspected bleeding disorder, including a history of prolonged bleeding, except for the use of anticoagulation for deep vein thrombosis (DVT) prophylaxis (e.g., postoperative DVT prophylaxis) or the use of low dose acetylsalicylic acid (≤ 325 mg).

Study Intervention Clinic Locations: All participating ANC and OPD clinics in the DCP trial will offer CAB-LA. For VHT/CHV communities, the nearest health facility will offer CAB-LA for all participants

- 1) In Uganda, the sites for each of the trials:
 - a. OPD: Itojo Hospital, Kitagata Hospital
 - b. ANC: Bwizibwera HCIV, Bushenyi HCIV
 - c. VHT: Ndeija Health Center III
- 2) In Kenya, the sites for each of the trials:
 - a. OPD: Magunga Level IV Hospital, Oyani Hospital
 - b. ANC: Oyani Hospital, Sena Health Centre

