Reach (Participant level)	Proportion of eligible participants who initiate CAB-LA weeks 0-48. Characteristics (including prior PrEP and PEP use) and attitudes (knowledge, acceptability and feasibility) of participants using CAB-LA	Demographics, CAB-LA dispensing logs Knowledge, Acceptability and Feasibility (Survey and IDI). Evaluation includes focus on equitable access by gender, education and SES.	CAB LA dispensing throughout follow-up Surveys and IDI: Week 0, 24 and week 48
Effectiveness (Participant level)	Impact of adding CAB-LA to Dynamic choice prevention on biomedical covered time (comparison of follow-up during the CAB-LA extension vs. follow-up time in Phase A trials prior to CAB-LA extension).	CAB-LA dispensing logs, PrEP and PEP use as defined for primary endpoint in extension.	Throughout follow-up
Adoption (Provider and staff level in different settings)	% of staff and providers invited that participate in the interventions, where participation is defined as i) participation in CAB-LA trainings; and ii) offering CAB-LA to participants. We will further assess the characteristics of participant vs. non-participant staff.	Training attendance rosters; CAB-LA dispensing logs	Throughout follow-up
Implementation (Provider and systems level)	Fidelity: Proportion of providers offering CAB-LA on appropriate schedule, appropriate provision of oral bridging Costing: Incremental cost of adding CAB-LA to dynamic choice prevention Adaptations: Type, timing and reasons they were made	CAB-LA and oral bridging dispensing logs Time in motion and program costing Adaptation logs	Throughout follow-up
Maintenance (adapted from standard RE-AIM to accommodate shorter follow-up) (Participant level)	Persistence on CAB-LA among participants who initiate CAB-LA Reasons for discontinuation of biomedical prevention or switching to other biomedical prevention option	CAB-LA dispensing logs Participant survey on reasons for discontinuation and switching	Throughout follow up

As a tertiary objective, we will also assess provider and staff Knowledge, Acceptability and Awareness via provider and staff surveys (Likert scales) and IDI at weeks 0, 24, and 48.

D. Schedule of Evaluations

For all participants, from the time of reconsenting at the start of study CAB-LA availability (Week 0), there will be study visits every 24 weeks for the duration of their participation.

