The primary study endpoint in this extension will be biomedical covered time defined as the proportion of follow-up time that the participant is protected from HIV infection by any PEP or PrEP (inclusive of CAB-LA). Follow-up will be over the 48 weeks following re-consent for the CAB-LA extension. At risk covered time will be a secondary outcome, defined as the proportion of at-risk follow-up time that the participant is protected from HIV infection by any PEP or PrEP (inclusive of CAB-LA). We will also conduct sensitivity analyses, varying the definitions of coverage and risk. For example, we will also examine covered time from CAB-LA only (i.e., exclusive of oral PrEP or PEP), and we will conduct a sensitivity analysis in which we treat time after loss to follow-up among persons not known to have moved out of the study region and time after study withdrawal as presumed to be non-covered.

For our primary objective in this extension, we will compare covered time during the 48 week CAB-LA extension between the intervention and control arms. For improved efficiency, Targeted Maximum Likelihood Estimation (TMLE) will be used to adjust for differences in baseline participant characteristics between the two trial arms, accounting for the stratified randomization design. In secondary analyses, we will further use TMLE to i) adjust for measured differences between arms at time of start of the CAB-LA extension period; and, ii) adjust for baseline and time-varying factors that are predictive of the outcome and that differ between persons that do vs. do not have their follow-up time censored. The primary analysis will pool over the trials, accounting for clustering inherent in the community trial; secondary analyses will stratify by trial site. We will test the null hypothesis that covered time is the same between arms with a two-sided test at the 5% significance level.

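### Does the CAB-LA extension need its own rule on whether participants enrolled as replacements after 1 September 2021 are analysed?

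*Protocol*

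**What the plan says.** Protocol 15.2 states: "All analyses of Dynamic Prevention in Phase A will restrict to participants enrolled before September 1, 2021". Protocol 15.3 repeats the limit for the cluster trial: "Analyses of the VHT trial will restrict to participants enrolled before September 1, 2021".

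Appendix 18 describes the extension as a 48-week continuation of three ongoing Phase A trials. Beside an enrolment count dated 9 May 2022, Section A says "New participants are being enrolled at the present to time to replace those participants who have moved" and were unable to continue, and adds: "The total number of participants in the study eligible for CAB-LA will not exceed the 593 listed in Table 1". The first extension criterion is "Enrollment in a SEARCH Sapphire Dynamic prevention study". The others are HIV-negative status and residence in the study region, and none carries a date. On access to the drug, the appendix opening says "Persons in the control arms will be eligible to receive CAB-LA if and when it is rolled out through in country programs".

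Section H, which calls itself an overview, gives the primary comparison: "The primary analysis will pool over the trials, accounting for clustering inherent in the community trial". Table 4 defines the Effectiveness measure as a "comparison of follow-up during the CAB-LA extension vs. follow-up time in Phase A trials prior to CAB-LA extension". The power text lists continuing enrolment among the reasons its figures are conservative.

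**The concern.** The two parts of the protocol seem to point in different directions. Section 15 closes the analysis population at 1 September 2021. The appendix brings in people later, admits anyone enrolled in one of the three trials, and counts their arrival as a power reserve, which would be empty if they were left out. Section H does not say which holds. It also does not say whether control participants are replaced: 593 is the intervention-arm total.

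If replacements were analysed, the consequences would differ by analysis.

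- **Clinic trials.** Replacements randomised 1:1 would cause no expected bias.
- **Village trial.** The arm is fixed by village. A person approached in 2022 in an intervention village may be joining a study that offers CAB-LA, while a person in a control village is not. Willingness to join could differ by arm, and the pooled primary analysis would carry that difference.
- **Pre/post Effectiveness test.** Replacements would add extension time with little or no Phase A time before it, so the two periods would contain different people.

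**Working it through.** **1. What the text covers.** The limit in 15.2 applies to all Phase A Dynamic Prevention analyses, and the one in 15.3 to analyses of the village trial without qualification. The appendix places the three extended trials in Phase A and keeps people in the arm assigned at their initial visit. On the literal reading, replacements receive the intervention and follow-up but are not analysed, and both harms disappear.

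**2. Does the stated power depend on replacements?**

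*Clinic trials.* Inputs from the appendix power text: 90% consent, 90% retention, SD 0.35, two-sided 5%; about 200 per arm from Table 1. Evaluable: 200 × 0.9 × 0.9 = 162 per arm, the stated figure. A two-sample t-test for 11 points gives 80.5% power (detectable effect 10.9 points), which reproduces the stated >80%.

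*Village trial.* Matched-pair formula for means with c = 8 villages per arm:

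c = 2 + (1.96 + 0.84)² × [2σ²/m + k²(μ₀² + μ₁²)] / (μ₁ − μ₀)²

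Inputs: σ = 0.35, k = 0.25, μ₀ = 0.10. At m = 20 and a difference of 0.148: 2σ²/m = 0.01225; k²(0.10² + 0.248²) = 0.00447; c = 2 + 7.849 × 0.01672 / 0.0219 ≈ 8. The detectable effect is 14.8 points, which reproduces the stated 15.

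The village SAP reports 429 people enrolled May–August 2021, all before the limit. 429 × 0.81 / 16 = 21.7 per village, detectable effect 14.3 points. The assumed 20 or so is met without any replacement (this uses the arithmetic mean; the harmonic mean is not given).

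**3. What would replacements add?** The number is not stated, so two assumptions are shown.

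| Assumption | Clinic n/arm | Power for 11 points | Per village | Detectable effect |
|---|---|---|---|---|
| None analysed | 162 | 80.5% | 21.7 | 14.3 points |
| Non-consenters replaced | 180 | 84.5% | 429 × 0.9 / 16 = 24.1 | 13.7 points |
| Later losses also replaced | 200 | 88.0% | 429 / 16 = 26.8 | 13.1 points |

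Applying the limit forgoes up to 7.5 points of clinic power and 1.2 points of village detectable effect, all of it above what the plan claims.

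**4. Size of the bias if the limit did not apply.** By Table 1 the village trial is 410 of 1213 participants, 33.8%. With equal weight per participant, each point of village bias moves the pooled estimate by about 0.34 points. For illustration only, assume 10% of intervention-village participants are replacements whose coverage is 10 to 50 points above those they replace. The village contrast then shifts by 0.10 × 10 = 1 to 0.10 × 50 = 5 points, and the pooled contrast by 0.3 to 1.7 points. With a pooled standard error of about 2.3 points, the pooled type I error would be about 5% to 12%. Nothing in the documents supports any value in that range.

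**5. Is village replacement visible?** Table 1 lists 401 antenatal, 402 outpatient and 410 village participants. The SAPs report 400, 403 and 429 originally enrolled. The village count is 19 lower, so no net addition appears there. This does not exclude some replacement after losses.

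**The case for a change.** The strongest case for a change is that both readings have support and only one can hold. If the limit applied, there would be little reason to cite continuing enrolment as a power reserve. Choosing the population after seeing data would be a post hoc decision on a primary result. The planned adjustments use measured factors only: the TMLE that adjusts for arm differences at the start of the extension is secondary, and no adjustment supplies a pre-period that a person never had.

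The ambiguity stands, and so does the stray remark in the power text. The rest weakens on inspection.

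- The original village cohort also enrolled after village allocation, so knowledge of the arm at enrolment is not new. Only the CAB-LA offer is, and its effect on who joins is conjecture.
- A restriction of the village contribution to people enrolled before September 2021 is what 15.3 already says. Keeping clinic replacements would depart from 15.2 if the limit applies.
- Table 4 already confines the comparator to Phase A time before the extension, and Section H plans a TMLE for serial measures with control-arm trends. Using people observed in both periods is the natural reading.
- Section H also plans analyses stratified by trial site, which would help show whether the village trial drives the pooled result.
- Section H is only an overview and the extension has its own registration. The prevention SAPs supplied cover the parent trials, so the absence here of an extension SAP does not show that the population is undefined.

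**Conclusion.** No change to the plan is needed. The appendix omits a cross-reference, and the protocol's existing date rule supplies the answer: read literally, nobody enrolled from 1 September 2021 onward is analysed, and the bias from replacements is nil. The stated power holds under that rule (80.5% for 11 points in each clinic trial; a detectable effect of 14.3 points against the stated 15 in the village trial), assuming 90% consent, 90% retention and village sizes near their mean.

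If the sponsor intends the other reading, clinic replacements are harmless provided they are randomised 1:1. Any village bias enters the pooled estimate at about one third of its size. Its amount is unknown, and no village replacement is documented. An analyst who applies 15.2 and 15.3 as written, and uses intervention participants with Phase A follow-up for the pre/post comparison, reaches a sound analysis without further instruction.
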